**11.2 Sample Size:**

62

**11.3 Total number of subjects requested (including records and specimens):**

62

**11.4 If you are recruiting by study arm, please identify the arms of the study and how many subjects will be enrolled in each arm**

Experimental arm (Ketamine) - 31 subjects  
 Placebo arm (saline) - 31 subjects

**11.5 Please provide a justification for your sample size**

Number of Subjects and Justification

This trial aims to have a minimum of 62 individuals. N calculation was done using R's built in statistical power pack. (Appendix D: N Calculation) Significance level and power used were the standard 0.05 and 0.8 respectively. Prior studies showed very large effect sizes. Their Cohen's d within groups and between groups were 1.23 and 1.45 respectively. The power of a study depends on effect size as well as sample size. Because their effect size is sufficiently large, they are able to detect differences from even a small sample.

When using this effect size, N calculations resulted in 8.5 to 11.4 individuals, which correlates to 17 to 22.8 individuals. However, the design of our study varies from past studies, in that we include a broader patient population. Instead of simply at individuals diagnosed with a mood disorder.

Based on suggested Cohen's d values, in order to have a large effect size in the T-test and ANOVA tests, N should be 25.5. In order to determine large correlations, N needs to be at least 28.2. This correlates to 52 to 56 subjects. Applying an estimated 10% subject dropout rate, the estimated number of subjects needed for the study is 62. Full effect and sample size breakdown are shown in Table 4.

**Table 4:** Effect and Sample Size Breakdown

| Test              | Effect size                     | N    |
|-------------------|---------------------------------|------|
| Two sample T-Test | Large (d = 0.8)                 | 25.5 |
| Two sample T-Test | Medium (d = 0.5)                | 63.7 |
| Two sample T-Test | Average within groups (d=1.23)  | 11.4 |
| Two sample T-Test | Average between groups (d=1.45) | 8.5  |
| ANOVA             | Large (f = 0.4)                 | 25.5 |
| ANOVA             | Medium (f = 0.25)               | 63.7 |

A Linear model will be used for analysis of repeat measures if sample size reach 74 subjects. This model accounts for uneven spacing in repeated measures, accounts for random effects, will provide a greater flexibility in analysis. The ability of this analysis is limited by the degree of freedom, which is influenced by the sample size. R separates the F test into two variables representing the degree of freedom of the model and error, which are the numerator and the denominators in the F test. In this test, the numerator (u) is the number of observations, and is equal to  $p - 1$ , where  $p$  is the number of predictors (sex, age, etc....). The denominator (v) is the degree of freedom of the error and is equal to  $n - p$ , where  $n$  is the number of observations, or, in our case, subjects. Sample Calculation 1 was used to determine  $n$  need to power a model that would take into account three to five predictors. (Table 5)

Sample Calculation 1:

$$u = p - 1 \rightarrow u + 1 = p$$

$$v = n - p \rightarrow v + p = n$$

To solve for  $n$ :

$$v + u + 1 = n$$

**Table 5:** N needed to power Linear model with a large effect size ( $f^2 = 0.35$ )

| Numerator (u) | Denominator (v) | n | 2n |
|---------------|-----------------|---|----|
|               |                 |   |    |

|   |    |    |    |
|---|----|----|----|
| 5 | 37 | 43 | 86 |
| 4 | 34 | 37 | 74 |
| 3 | 31 | 35 | 70 |

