### 11.6 Data Analysis Plan: Complete description: Background, Objectives, Design, Step by Step how the project is going to be done, Data analysis plan:

**Table 6:** Test Plan of Data Analysis

| Question to be answered   | Type of Analysis                                   | Independent (x)  | Dependent (y)      | Relationship     |
|---|--|--|--------------------|------------------|
| Is there a difference effect of ketamine in those who are high suicide vs. high depressed?                  | McNemar test                                       | High Suicide   | High depressed     | Within           |
| Is there a difference in the placebo between the same two groups?   | McNemar test                                       | High Suicide group                                     | High Suicide group | Within           |
| Is there any difference between ketamine vs. placebo on BSSI & MADRS?                                       | One-way MANOVA                                     | Group  | BSSI; MADRS        | Between          |
| Is there a difference in SI between Ketamine vs placebo   | 2 Independent sample t test                        | Group  | BSSI @ T4          | Between          |
| Is there a difference in depression between Ketamine vs placebo   | 2 independent sample t test                        | Group  | MADRS @ T4         | Between          |
| Is there a difference in effect from placebo when accounting for covariates?                                | MANCOVA  | Fixed factor: Group
Covariates: Demographics        | BSSI, MADRS @ T4   | Between          |
| Is there a difference in effect from ketamine @ the different time points?                                  | Mixed model
Or
Repeated measure ANOVA | Fixed factor: Group                                    | BSSI               | Within & between |
| Is there a difference in group at the different time points, when MADRS is a covariate?                     | Mixed model                                 | Fixed factor: Group
Covariates: MADRS               | BSSI               | Within & between |
| Is there a difference in group at the different time points, when MADRS, and demographics are considered? * | Mixed model                                 | Fixed factor: Group
Covariates: MADRS, demographics | BSSI               | Within & between |

\*This case requires a larger sample size.

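### The 74-subject condition for the repeated-measures linear model double counts a sample size that is already the trial total, and does not fit the MADRS-covariate row of Table 6

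*Combined protocol and SAP*

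**What the plan says.** Section 11.5 makes the choice of repeated-measures model depend on the number of subjects: "A Linear model will be used for analysis of repeat measures if sample size reach 74 subjects". It gives its reason for preferring this model: "This model accounts for uneven spacing in repeated measures, accounts for random effects". The size condition comes from an F-test calculation intended for "a model that would take into account three to five predictors". Sample Calculation 1 sets u = p - 1 and v = n - p, hence n = v + u + 1, and the text says that n counts subjects. Table 5 of Section 11.5 (f2 = 0.35) prints three rows of u, v, n and 2n: 5, 37, 43, 86; 4, 34, 37, 74; and 3, 31, 35, 70.

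The total requested is 62, in two equal arms: Section 11.4 gives "Experimental arm (Ketamine) - 31 subjects" and the same number on saline.

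Table 6 in Section 11.6 has three mixed-model rows for BSSI, each with group as a fixed factor:
- The unadjusted row offers a mixed model or repeated-measures ANOVA.
- The row "Is there a difference in group at the different time points, when MADRS is a covariate" lists a mixed model only and has no footnote.
- The row with MADRS and demographics carries the footnote "This case requires a larger sample size".

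**The concern.** A threshold of 74 lies 12 above the 62 subjects requested (74 - 62 = 12), so a trial that enrols as planned never reaches it. The threshold therefore acts as a decision rule. At 62 it turns the repeated-measures analysis away from the model that Section 11.5 itself favours. The assessments are at baseline, 4 hours, 24 hours and one week, so the uneven spacing that motivates this preference is real, and the analysis bears on durability of effect (Specific aim 2). If the threshold is an arithmetic error, an error is choosing the analysis. It also leaves Section 11.5 and one row of Table 6 giving different answers about whether the mixed model will be fitted at 62.

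**Working it through.** **Inputs.** Alpha 0.05, power 0.80, 62 subjects and 10% dropout (Sections 11.2 to 11.5); f2 = 0.35 and u = 3, 4, 5 (Table 5); n = v + u + 1 (Sample Calculation 1).

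**Step 1: reproduce the plan's v.** Power = P(F' > Fcrit), where F' is noncentral F with u and v degrees of freedom and noncentrality f2 × (u + v + 1), and Fcrit is the upper 5% point of the central F. Solving for 80% power:

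| u | v solved | v printed | v + u + 1 from printed v | n printed | 2n printed |
|---|---|---|---|---|---|
| 3 | 31.31 | 31 | 35 | 35 | 70 |
| 4 | 34.15 | 34 | 39 | 37 | 74 |
| 5 | 36.54 | 37 | 43 | 43 | 86 |

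The v column reproduces, so this is the test the plan used. The u = 4 row does not follow the plan's own formula: 34 + 4 + 1 = 39, not 37. Doubled, that would be 78, so 74 is wrong even if doubling were right.

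**Step 2: what n counts.** In v = n - p, v is the error degrees of freedom of one fitted model, so n is every subject in that model. Table 6 has group as a fixed factor in each mixed-model row, so both arms are in it and n is the trial total. Doubling suits the t-test figures of Table 4, which are per arm: for d = 0.8 the recomputed value is 25.52 per arm, against 25.5 printed. It does not suit Table 5.

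**Step 3: trial totals without doubling.**

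| u | n solved | n rounded up | power at that n | power at 56 | power at 62 |
|---|---|---|---|---|---|
| 3 | 35.31 | 36 | 0.810 | 0.961 | 0.977 |
| 4 | 39.15 | 40 | 0.811 | 0.941 | 0.964 |
| 5 | 42.54 | 43 | 0.806 | 0.920 | 0.949 |

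The 56 is 62 × 0.9 = 55.8. With v rounded to the nearest integer, as the plan does, the totals are 35, 39 and 43, with power 0.796, 0.798 and 0.806. At 74 subjects the u = 4 test has power 0.987, not 0.80.

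**Step 4: dependence on the effect size.** The documents give no smaller f2 for this model. At an assumed f2 = 0.15, power at 62 is 0.69, 0.64 and 0.59 for u = 3, 4 and 5.

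**Step 5: Section 11.5 against Table 6 at 62 subjects.**
- Unadjusted row: no conflict. It offers two methods, and the condition in Section 11.5 chooses between them.
- MADRS-plus-demographics row: no conflict. Its footnote already asks for a larger sample.
- MADRS-covariate row: inconsistent. It lists a mixed model, with no alternative and no size condition, while Section 11.5 ties that model to 74.

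**The case against.** **A possible reconciliation.** Group plus MADRS could be read as u = 2. Then v rounds up to 28, n = 28 + 2 + 1 = 31 and 2n = 62, which would match the planned total. However, Table 5 has no u = 2 row, Section 11.5 states the 74 condition without exception, and the doubling would still be wrong.

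**The condition is not a ban.** Section 11.5 says the model will be used if 74 is reached. It does not expressly forbid it below that. This stands. A reader might infer that the MADRS-covariate question is left with no permitted analysis, but the documents support only an unresolved inconsistency.

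**The u values.** A reader might also infer from u = p - 1 that three to five predictors means u = 2 to 4, so that Table 5 lists the wrong rows. That is not the better reading. With an intercept in the model, k predictor terms give k numerator degrees of freedom, so u = 3 to 5 is right. The loose item is the description of p as the number of predictors; n = v + u + 1 needs p to include the intercept.

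**Power.** The most tempting stronger reading is that 62 subjects are shown to be enough for the mixed model. They are not. Table 5 is a joint test of all u terms at a large effect, with one observation per subject. It says nothing about within-subject correlation or the group-by-time effect, and Step 4 shows how far it rests on f2 = 0.35.

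**Reach.** The t tests, MANOVA and MANCOVA in Table 6 are not tied to 74, and the unadjusted row keeps a permitted alternative. This also stands, and it limits the consequence.

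**Conclusion.** The 74-subject condition has no basis in the plan's own calculation. It comes from doubling an n that is already the trial total, in a row that is also mis-added by 2. On the plan's criterion the totals are 36, 40 and 43 for u = 3, 4 and 5, against 62 requested and about 56 evaluable. At 62 the condition directs the repeated-measures analysis away from the preferred model and is inconsistent with one row of Table 6, the one with MADRS as covariate.

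This rests on one model containing both arms, as Table 6 specifies, and on f2 = 0.35, alpha 0.05 and power 0.80 as stated. It does not establish adequate power for the mixed model or for group-by-time at 62. A reader might also infer that the enrolment target is wrong. The correction concerns only the 74 threshold: it does not itself change the target, and the derivation of 62 was not assessed here. The point should be corrected before analysis, but it does not affect the between-group tests.

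**What to change.** 1. **Section 11.5:** delete the 74-subject condition and name the mixed model for the repeated-measures analysis of BSSI at the planned N. Make the unadjusted and MADRS-covariate rows of Table 6 agree with this. Repeated-measures ANOVA may stay as a supporting analysis.
2. **Table 5 of Section 11.5:** remove the 2n column, state that n is the trial total, and keep u = 3, 4, 5 with n = 36, 40, 43. Reword p as the number of model parameters including the intercept, so that u is the number of predictor terms.
3. **Add a limit beside Table 5:** it is a fixed-effects F test at f2 = 0.35, it ignores within-subject correlation, and it does not power the group-by-time effect.
4. **Footnoted row of Table 6:** re-derive its size condition from the corrected Table 5, or label the row exploratory.

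The cost is revised analysis-plan wording and a corrected table. Visits and data collection do not change, and the enrolment target is not altered by this correction.

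### Table 5 in section 11.5 powers the joint F test of all predictors, but the mixed models are meant to test Group, so its 74-subject condition does not reflect power for ketamine

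*Combined protocol and SAP*

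**What the plan says.** Section 11.5 states a condition for the repeated-measures analysis: "A Linear model will be used for analysis of repeat measures if sample size reach 74 subjects". The figure comes from Sample Calculation 1 and Table 5 of the same section (not the other Table 5, on ketamine intoxication, in section 16.1). Their stated purpose is to find the n "need to power a model that would take into account three to five predictors".

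The section describes the two F-test quantities as "representing the degree of freedom of the model and error, which are the numerator and the denominators in the F test". It sets u = p − 1, where p counts predictors such as sex and age, and v = n − p, so n = v + u + 1. The effect size is f² = 0.35, labelled large. The printed rows (u, v, n, 2n) are 5, 37, 43, 86; 4, 34, 37, 74; and 3, 31, 35, 70. No effect size or degrees of freedom are given for treatment alone.

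Earlier in 11.5, for the sample size in general: "Significance level and power used were the standard 0.05 and 0.8 respectively". These values are not repeated beside Table 5.

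Table 6 in section 11.6 sets out what the mixed models are for. One row asks: "Is there a difference in group at the different time points, when MADRS is a covariate"; another adds demographics. In each mixed-model row the fixed factor is Group and the outcome is BSSI. No row asks whether the predictors matter jointly.

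The planned size is 62, 31 per arm (sections 11.2 to 11.4). It is justified from t-test and ANOVA entries at a large effect (d = 0.8, 25.5 per arm) and a correlation calculation, plus 10% dropout.

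**The concern.** The overall F test and the Group test have different nulls. The overall F is rejected if any predictor is related to BSSI. A depression score or age could produce that result when ketamine does nothing. An 80% chance of rejecting the joint null is therefore not an 80% chance of detecting ketamine, and it cannot be converted into one without an assumption about how much of f² = 0.35 belongs to Group. The plan states no such assumption.

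This matters because Table 5 is used as a decision rule. Section 11.5 credits the linear model with handling unevenly spaced measurements and random effects, and whether it may be used is settled by a calculation for a hypothesis that Table 6 never poses.

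**Working it through.** **Step 1. Reproduce Table 5.** Inputs from 11.5: f² = 0.35, significance level 0.05, power 0.80, u = 3, 4, 5. Use the noncentral F with u and v degrees of freedom and noncentrality λ = f²(u + v + 1), and solve for v at 80% power.

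| u | v solved | v in Table 5 | Joint power at Table 5's v |
|---|---|---|---|
| 3 | 31.3 | 31 | 79.6% |
| 4 | 34.1 | 34 | 79.8% |
| 5 | 36.5 | 37 | 80.6% |

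The same equation with u = 1 gives v = 22.5, which is not in the table. So Table 5 is the joint test on all u degrees of freedom. The match also indicates that the general 0.05 and 0.8 apply to it.

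**Step 2. What Table 5 implies for Group.** Take N = 74 and four predictors, so error df = 74 − 4 − 1 = 69. Test Group on 1 df with λ = (share × 0.35) × 74. The share of f² due to Group is my assumption, with predictors taken as uncorrelated.

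| Group's share of f² | Power for Group |
|---|---|
| 100% | 99.9% |
| 50% | 94.4% |
| 25% | 70.9% |
| 10% | 35.5% |
| 0% | 5% |

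Joint power at N = 74 is 98.7% in every row. Table 5 therefore leaves power for Group undefined.

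**Step 3. Power for Group at the plan's own effect.** With 1:1 allocation and d in residual-SD units, f² = d²/4 = 0.64/4 = 0.16. With four predictors, error df = N − 5 and λ = 0.16 × N.

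| Total N | Error df | λ | Power for Group |
|---|---|---|---|
| 52 | 47 | 8.32 | 80.7% |
| 62 | 57 | 9.92 | 87.2% |
| 74 | 69 | 11.84 | 92.4% |

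The total needed for 80% power solves to 51.2, so 52. With 10% dropout, 62 × 0.9 = 55.8, which is still above 52.

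**Step 4. Why 74 exceeds 62.** In this regression n is already the total number of subjects. Table 5 doubles it, and 74 = 2 × 37. The u = 4 row also breaks its own formula: 4 + 34 + 1 = 39, not 37. Undoubled and with that sum corrected, the joint test asks for 35, 39 or 43 subjects, all below 62. The doubling and the addition are separate errors; correcting both would still leave a calculation for the joint null.

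**The case against.** The strongest reply is that nothing turns on this. The planned 62 does not come from Table 5, and the t test behind it is a comparison of the two groups. The barrier at 74 comes from doubling. Without the doubling, 62 passes whether the joint test (35 to 43) or the Group test (about 52) is used, and at d = 0.8 the Group test is the more demanding of the two. All of this stands, and it limits the point to the basis of a decision rule. It does not make Table 5 a calculation for the question in Table 6, and the 74-subject condition remains in the plan.

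It is also true that section 11.5 speaks of powering a model and nowhere claims 80% power for ketamine. The defect is that the power for the treatment term is missing, not that a false figure is stated for it.

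A further fair reply is that a 1-df regression on one observation per subject is not the planned analysis either. Table 6 asks about groups at the different time points and marks these rows as within and between, which may mean Group-by-time. That stands, and it shapes the fix.

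A reader might infer that the trial is underpowered for ketamine, or that the joint test is what puts the preferred model out of reach. The documents support neither. The first would need a small assumed share of f² for Group, which the plan does not give; the second is explained by the doubling.

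**Conclusion.** The point holds in a limited form. Table 5 in section 11.5 is the overall F test on 3 to 5 degrees of freedom, while the mixed models it governs are used to ask about Group. It gives no power for the ketamine effect: at N = 74 that power could be anything from 5% to 99.9%, depending on a share of f² that the plan does not state. The 74-subject condition therefore rests on the wrong hypothesis.

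No shortfall is shown. At the plan's own d = 0.8, a 1-df Group test with four predictors has about 87% power at 62 and 92% at 74, and 80% is reached at about 52 in total. These figures assume 1:1 allocation, d in residual-SD units, covariates uncorrelated with Group, and one observation per subject. They ignore within-subject correlation, as Table 5 does, and would not carry over unchanged to a Group-by-time test.

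**What to change.** Replace Sample Calculation 1 and Table 5 in section 11.5 with a calculation for the treatment term that the mixed model will test:

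- Name the term: Group, or Group-by-time if that is the question in Table 6, and give its numerator degrees of freedom.
- Use the effect size used elsewhere in 11.5 (d = 0.8, so f² = 0.16 for a 1-df Group test). Count the other predictors only in the error degrees of freedom, and take n as the total.
- Either state that the single-observation figure ignores within-subject correlation, or include that correlation with a stated assumed value.
- Replace the 74-subject condition with one based on this calculation. For the 1-df Group test at d = 0.8, the planned 62 is enough.

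The cost is a recalculation, a replaced table and a revised sentence in 11.5. No extra patients or data are needed.

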### 11.6 Data Analysis Plan: Complete description: Background, Objectives, Design, Step by Step how the project is going to be done, Data analysis plan:

**Table 6:** Test Plan of Data Analysis

| Question to be answered   | Type of Analysis                                   | Independent (x)  | Dependent (y)      | Relationship     |
|---|--|--|--------------------|------------------|
| Is there a difference effect of ketamine in those who are high suicide vs. high depressed?                  | McNemar test                                       | High Suicide   | High depressed     | Within           |
| Is there a difference in the placebo between the same two groups?   | McNemar test                                       | High Suicide group                                     | High Suicide group | Within           |
| Is there any difference between ketamine vs. placebo on BSSI & MADRS?                                       | One-way MANOVA                                     | Group  | BSSI; MADRS        | Between          |
| Is there a difference in SI between Ketamine vs placebo   | 2 Independent sample t test                        | Group  | BSSI @ T4          | Between          |
| Is there a difference in depression between Ketamine vs placebo   | 2 independent sample t test                        | Group  | MADRS @ T4         | Between          |
| Is there a difference in effect from placebo when accounting for covariates?                                | MANCOVA  | Fixed factor: Group
Covariates: Demographics        | BSSI, MADRS @ T4   | Between          |
| Is there a difference in effect from ketamine @ the different time points?                                  | Mixed model
Or
Repeated measure ANOVA | Fixed factor: Group                                    | BSSI               | Within & between |
| Is there a difference in group at the different time points, when MADRS is a covariate?                     | Mixed model                                 | Fixed factor: Group
Covariates: MADRS               | BSSI               | Within & between |
| Is there a difference in group at the different time points, when MADRS, and demographics are considered? * | Mixed model                                 | Fixed factor: Group
Covariates: MADRS, demographics | BSSI               | Within & between |

\*This case requires a larger sample size.

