The BSSI will measure the severity of SI. It is based on the interviewer rated version of the original Scale for Suicidal Ideation (SSI), which is one of the few document suicide assessment tools with predictive validity for suicide completion.42 The internal reliability, test and retest validity, as well as invariance over time has been demonstrated for the BSS. 43, 45 Furthermore, the first five items of the BSSI are a common clinical screening for the presence of suicidal thoughts.40 For these reasons, the BSSI was chosen as our primary outcomes measure. Two studies have indicated that the cut off between high and low risk is a BSS  $\geq 2$ .43, 45 A recent investigation has determined BSSI  $\geq 6$  is predictive of future suicide attempts. 53 These two values will serve in our analysis.

The Montgomery- Åsberg Depression Rating Scale (MADRS) is a widely known 10 item clinician administered measure of depression severity.46 Since its development in the late 1970s, it has become more popular than the gold standard, Hamilton rating scale for Depression (HAM-D). It is considered to be more sensitive to change, just as effective, and simpler to use clinically.47 However, the reliability depends on good interrater agreement.48 Difficulties in clinical trial to show signal detection for known effective drugs have implicated clinician administered measurement as a possible source of error. To avoid poor interrater reliability, rater bias, and variable interview quality,48 this trial will utilize the self-administered version of the MADRS-S.49 This has 9 items and

a total score ranging from 0 to 27.50 The scoring of MADRS-S has shown to be similar to that of physician scoring.

The emotional pain of the suicidal patient requires empathetic care that may not always be possible with the time pressures, volume, and pragmatic nature of the ED environment. A pharmacologic intervention with rapid effects to decrease SI would play a vital role in improving the standard of care for this vulnerable population.

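### Table 6 rows 1 and 2: the within-arm McNemar tests do not answer the questions set for them, because they cannot separate a ketamine effect from how common two labels are

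*Combined protocol and SAP*

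**What the plan says.** Table 6 in section 11.6 opens with two McNemar rows, both marked as within-group.

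- Row 1 asks "Is there a difference effect of ketamine in those who are high suicide vs. high depressed". Its independent variable is the high-suicide label and its dependent variable the high-depressed label.
- Row 2 asks "Is there a difference in the placebo between the same two groups". The high-suicide group is printed as both the independent and the dependent variable.

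Neither row names the study arm as a factor, a baseline value or a time point. The other seven rows (MANOVA, two t tests, MANCOVA, three mixed-model or repeated-measures rows) use BSSI and/or MADRS with no high/low split.

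Section 9.2 names two BSSI thresholds, 2 or more and 6 or more, and says of them: "These two values will serve in our analysis". Section 11.1 mentions a threshold of 2 on an average of four items, but only to justify a rule on incomplete questionnaires. The high-suicide label is not tied to any of these values. No MADRS-S threshold for the high-depressed label is given; section 9.2 states only the 0 to 27 range.

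**The concern.** Row 1 poses a question about treatment effect: does ketamine act differently on, or in, two kinds of patient? McNemar's test answers a different one. It takes two yes/no labels on the same people and tests whether they are equally frequent. Applied to ketamine patients alone, its result turns on where the two thresholds are set and how common each state is in people admitted with active suicidal ideation.

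For row 2, a label paired with itself can never disagree with itself, so the test carries no information. If the second variable should have been the high-depressed label, the row repeats row 1 in the placebo arm. A reader would then have a ketamine p-value and a placebo p-value side by side, and that is not a test of the difference between arms.

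These are the first two questions in the analysis table. A significant row 1 could be reported as a differential effect of ketamine when none exists. They are also the only rows with high/low categories, so the thresholds from section 9.2 never enter a comparison of ketamine with placebo.

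**Working it through.** **Inputs from the plan.** Section 11.5: "Significance level and power used were the standard 0.05 and 0.8 respectively"; "in order to have a large effect size in the T-test and ANOVA tests, N should be 25.5". The same section gives a minimum of 28.2 for a large correlation, and then adds the allowance for losses: "Applying an estimated 10% subject dropout rate, the estimated number of subjects needed for the study is 62". Section 11.4: "Experimental arm (Ketamine) - 31 subjects", with the same number on placebo.

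**The plan's own figure.** Two-sided 0.05 and power 0.80 give 25.52 per group for d = 0.8 and for f = 0.4 with two groups. The correlation formula with r = 0.5 gives 28.25. Doubling 28, as the plan does, gives 56. Then 56/0.9 = 62.2 and 56 × 1.1 = 61.6, so 62 is reproduced. It rests on t-test, ANOVA and correlation inputs, not on any binary outcome. After 10% dropout, 31 × 0.9 = 27.9, so I use 28 per arm.

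**Assumptions, because the documents give no figures.** Label prevalences are as shown in the table. The correlation is 0.3, 0.5 or 0.7 between the underlying (latent) scores. This is not the correlation between the two labels, which was about 0.14 to 0.38 in the no-effect rows. The largest possible label correlation is (min(p,q) − pq)/√[p(1−p)q(1−q)]:

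- prevalences 0.9 and 0.7: 0.07/√(0.09 × 0.21) = 0.51
- prevalences 0.9 and 0.6: 0.06/√(0.09 × 0.24) = 0.41

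**Row 1, exact McNemar.** Let b and c be the counts of patients with only one of the two labels. The p-value is min(1, 2·P[Bin(b+c, ½) ≤ min(b,c)]). Rejection rates at 0.05, n = 28, by full enumeration:

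| Truth in the ketamine arm | Prevalences tested | Latent r = 0.3 / 0.5 / 0.7 |
|---|---|---|
| No drug effect | 0.9 vs 0.7 | 36.5% / 40.0% / 44.5% |
| No drug effect | 0.9 vs 0.6 | 71.2% / 77.0% / 83.4% |
| Both labels fall from 0.9 to 0.5 | 0.5 vs 0.5 | 2.4% / 2.2% / 1.7% |
| One label falls from 0.9 to 0.5, the other stays at 0.9 | 0.5 vs 0.9 | 92.2% / 95.4% / 97.8% |

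To see where a no-effect rejection comes from, take 0.9 vs 0.6 with r = 0.5. The discordant probabilities are 0.324 and 0.024, so about 28 × 0.324 = 9.1 and 28 × 0.024 = 0.7 patients are expected. A table with 9 against 1 gives p = 2 × (1 + 10)/1024 = 0.021.

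The last line of the table also shows the confounding. Labels at 0.5 and 0.9 give the same rejection rate whether ketamine moved one of them there or they stood there at baseline. Nothing in the row distinguishes the two.

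Sensitivity: with n = 31 and a label correlation of 0 to 0.3, the no-effect rejection rate at 0.9 vs 0.6 is 70% to 86%.

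**Row 2.** As printed, b = c = 0 for any data, and the exact test returns p = 1.

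**Between-arm alternative.** Power of Fisher's exact test with 28 per arm, two-sided 0.05, for assumed proportions at or above a BSSI cut-off:

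| Placebo vs ketamine | Power |
|---|---|
| 0.9 vs 0.5 | 0.89 |
| 0.9 vs 0.6 | 0.66 |
| 0.8 vs 0.5 | 0.57 |
| 0.7 vs 0.4 | 0.51 |
| 0.9 vs 0.7 | 0.33 |

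**The case against.** Several points on the other side are fair.

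- **A reader might infer that row 1 can never respond to ketamine.** That goes too far. If ketamine moves one label and not the other, the test rejects in 92% to 98% of trials. What stands is that the result cannot be attributed to the drug.
- **Row 2 is probably a copying slip.** Its wording refers back to the two groups of row 1, so the second variable was likely meant to be the high-depressed label. It is also not uncomputable, since the exact test gives p = 1. One label on both axes could even mean before versus after, which is a normal use of McNemar. But no time point is listed. A within-arm fall is also expected without any drug effect, because patients enter with active ideation (section 12.5) and both arms receive admission and therapy (section 10.1).
- **Section 9.2 does not promise a between-arm test on the cut-offs.** It says only that the values will be used in the analysis, and they may simply be meant to define the high-suicide label. Nor does Hypothesis 1 define clinical significance by a cut-off. What stands is that their role is unspecified and that no comparison of arms uses them.
- **Appendix D, not available here, may define the labels.** That would not add an arm, a baseline or a time point to the rows.
- **The alternative is not powerful.** The Fisher figures above show this, and the fix takes account of it.

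**Conclusion.** Rows 1 and 2 are wrong as written, not merely short of detail. Row 1 tests label prevalence in one arm under a question about a differential drug effect. Row 2 is uninformative if taken literally and shares row 1's flaw if corrected. Under the assumed prevalences, row 1 can reject in about 37% to 83% of trials with no drug effect and in about 2% when both labels fall by 40 points. Those percentages depend on assumed prevalences and latent correlations; the structural fault does not.

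A reader might conclude that the trial has no valid test of ketamine, or that the sample size fails. The documents support neither. Table 6 contains between-arm tests of BSSI scores in the MANOVA, t-test, MANCOVA and mixed-model rows, and 62 was not derived from McNemar. The harm is confined to these two questions and to the unused cut-offs. They should be corrected before analysis.

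**What to change.** Replace both rows of Table 6.

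1. **Differential effect.** Fit a linear model (ANCOVA) for BSSI at 24 hours with arm, baseline BSSI, baseline MADRS-S and mood-disorder history. Add the arm-by-baseline-BSSI and arm-by-baseline-MADRS-S interactions. Report them as exploratory estimates with 95% confidence intervals. State that the 74-subject condition in section 11.5, which is written for the repeated-measures linear model, does not govern this single-time-point model.
2. **Cut-offs, as a supportive analysis.** Report the proportion below each of the two section 9.2 thresholds (2 and 6) at 24 hours, ketamine versus placebo, stratified by mood-disorder history, with the risk difference and 95% confidence interval. State that these apply to the BSSI score as used in section 9.2, and keep them apart from the four-item average in section 11.1.

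The cost is two table rows and a few sentences in section 11.1. The data and the stratification factor are already planned, so nothing new is collected. The drawback is precision. The cut-off comparison has power of only 0.33 to 0.66 for the 20- and 30-point differences examined, and interactions will be poorly estimated at this size. Neither should serve as a confirmatory test.
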